#### **Improper working conditions**

The current version of the ACTIVA software is designed for exclusive use in the operating room with the equipment specified in the user manual. ACTIVA software should only be used with the propofol and remifentanil drugs for intravenous general anesthesia. The ACTIVA software must always be supervised by the primary experimenter and should not be used as a substitute for an anesthesiologist in any way.

#### **Factors that may compromise the outcome and interpretation of the results**

It is possible that the use of other sedative drugs in addition to propofol and remifentanil may affect the secondary objectives of the study, both in a negative and positive sense. The experimenter enters the use of such drugs in the notes of the ACTIVA software GUI, and this event remains recorded in the report file and will be considered during the analysis of the results.

It is possible that the experimenter may forget to enter events, drugs, or assessments relevant to the primary and secondary objectives in the notes of the ACTIVA software GUI. To minimize this risk, experimenters are trained according to the user manual and the current clinical protocol.

It is possible that the ACTIVA software, despite the pre-clinical development process and numerous simulations, does not meet reliability and safety criteria. In such a case, the study

#### **Clinical Investigation Plan**

Automatic Control of Total Intravenous Anesthesia: Closed-loop Delivery of Propofol and Remifentanil Using Bispectral Index as Feedback Variable.

Acronym: ACTIVA 2. Id code: NP-2861. NCT number: NCT04432974.

will be interrupted, and the manufacturer will assess for a prompt solution. Only after producing a reliable version of the ACTIVA software can the clinical investigation resume. It is possible that the monitor or one or both of the pumps may experience malfunctions during the clinical investigation. These malfunctions are not attributed to the ACTIVA software but will be recorded in the report file and evaluated during the results analysis. Repairing or replacing the faulty device resolves the issue.

It is possible that the primary experimenter may decide to discontinue the control system to switch to manual control or another anesthesiological technique, noting the choice, which will be recorded in the report file. Switching to manual control or another anesthesiological technique is possible at any time if the experimenter deems it appropriate, even in the absence of system malfunctions.

### Clinical investigation monitoring plan

The clinical investigation monitoring plan is the responsibility of the principal investigator and the advisory board specifically established for this clinical investigation. Monitoring of the clinical investigation ensures constant adherence to the clinical protocol by investigators and the application of all recommendations in this protocol.

The principal investigator and the advisory board verify that data is collected and stored adequately and reported correctly without alterations, in compliance with timelines, adequacy, accuracy, and truthfulness.

The task of the advisory board is to ensure that the investigation has sufficient and adequate investigators and resources to be conducted safely and effectively.

Monitoring of the clinical investigation occurs on a monthly basis for the following:

- Adequate preparation of investigators.
- Regular enrollment (informed consent and informational sheets).
- Evaluation of the ACTIVA software (with reference to primary outcome measure).
- Regular data collection and storage.
- Regular follow-up of enrolled subjects.
- Analysis of emerging issues as directed by the investigator.
- Analysis of safety-related notes regarding the ACTIVA software.

The principal investigator is required to maintain the report files generated by the ACTIVA software in their integrity and make them available to the competent Ethics Committee, the manufacturer, and the investigational site.

### Ethical considerations

Clinical experimentation was preceded by a careful phase of risk and benefit assessment resulting from the use of the control software under investigation. The main risk of the study

The patient is informed of the possibility to participate in the study during the preoperative anesthesiology visit, which usually takes place two weeks before the surgical procedure. On this occasion, the patient receives adequate information through an informative sheet and a discussion with the investigator. The informative sheet will then be retained by the patient. This document briefly describes the purpose of the study and its conduct, indicating the novelty of the clinical investigation compared to common clinical practice. If the patient intends to participate in the study, informed consent is signed before the start of the medical procedure subject to the experimentation.

## Data management

The data management activities have been carried out in such a way as to ensure that data processing is complete, consistent, and logical, and that all data described in the clinical investigation are included in the study. The file recorded by the ACTIVA control software allows for the analysis of the control system's performance regarding malfunctions and/or critical issues identified by the experimenter, recorded in the form of notes. Furthermore, it contains recordings of time series data for drug infusion rates, BIS (Bispectral Index), and other standard monitoring data for general anesthesia. The report file allows for offline analysis of the control system's performance. The report file is generated automatically by the ACTIVA control software. Post-operative data, on the other hand, are manually recorded by the experimenter on the designated data collection sheet. Experimenters have filled out the data collection sheet and entered notes on the GUI during the operation of the ACTIVA software as prescribed. During the conduct of the clinical study, the data resulting from the study are stored by the lead experimenter in their original form on the PC dedicated to the

## Clinical Investigation Plan

Automatic Control of Total Intravenous Anesthesia: Closed-loop Delivery of Propofol and Remifentanil Using Bispectral Index as Feedback Variable.

Acronym: ACTIVA 2. Id code: NP-2861. NCT number: NCT04432974.

ACTIVA software and backed up on the experimenter center's PC. At the end of the study, all data have been migrated and are stored on a dedicated PC at the experimenter center. Access to the data is restricted to authorized individuals.

## Amendments to the clinical evaluation plan

Any amendment to the protocol will be submitted to the competent authorities for authorization or appropriate notification, depending on the nature of the change. Additionally, all administrative updates that do not require submission to the competent authorities or the ethics committee will still be documented. An administrative update is defined as a change that has no impact on patient safety, health, or the scientific validity of the study.

## Deviations from the clinical evaluation plan

Except in cases of necessity, the principal investigator is not authorized to deviate from the clinical protocol. Deviations from the clinical evaluation plan that are decided upon by the investigator to protect the rights, safety, and health of the patient will be documented and communicated to the manufacturer and the sponsor as soon as possible.

The sponsor will define the level of deviations as major or minor and will present them to the relevant Ethics Committee for evaluation accordingly. Major deviations are defined as changes in the conduct of the clinical investigation compared to the current protocol that could compromise the subject's rights, safety, health, completeness, accuracy, or scientific integrity of the data.

Deviations should be reported to the principal investigator and recorded in the patient's chart. Cases where a regularly enrolled patient does not complete the study due to ACTIVA software issues or at the investigator's discretion are not considered deviations; the patient will not be considered for secondary outcome measures but will be evaluated for the primary outcome measure.

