The ACTIVA software always generates a report file, even in the case of malfunctions, containing all the data from patient monitoring, infusion pumps, and the software itself, along with notes entered by the principal investigator. Through data analysis, it is possible to identify the source of the technical issue.

In the event of ACTIVA software malfunction, the patient monitoring systems, particularly the Bispectral Index (BIS), are never altered or damaged (the data flow is only outbound to the computer where the ACTIVA software is installed), while the infusion pumps continue to operate in manual mode (standard/classic mode controlled by the anesthesiologist).

Switching to manual control is always possible at the discretion of the principal investigator, even in the absence of system malfunctions.

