## Information related to the clinical investigation

### Clinical study objectives

The primary objective of the clinical investigation is to investigate the clinical performances obtainable by the control system under study in terms of depth of hypnosis adequacy.

The secondary objective is to evaluate the reliability, safety and applicability of the control system under study and to carry out the clinical evaluation of the automatic control system during the induction, maintenance and recovery of general intravenous anesthesia.

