### Clinical study description

The clinical study ACTIVA 2 is a pragmatic, interventional, nonrandomized, single-arm, single-center.

The investigation is for research purposes (for publication in scientific journals), non-commercial, and for clinical development of the ACTIVA control software.

The primary outcome measure is the depth of hypnosis adequacy. It is assessed by means of the percentage of the anesthesia maintenance duration in which the BIS is kept inside the recommended range from 40 to 60. The percentage of the anesthesia maintenance duration in which the BIS is kept below 40 is also specified. Maintenance duration is the period of time that goes from the end of anesthesia induction to the point at which the automatic control is turned off at the conclusion of surgery. The end of anesthesia induction is defined as the time instant when the BIS drops below 40 for the first time and remains there for the subsequent 30 seconds.

The secondary outcomes measures are:

- Number and types of dysfunctions of the ACTIVA automatic infusion system.
- Level of satisfaction of the experimenter. It is expressed on a scale from 0 to 10 regarding the ease of use of the ACTIVA software and its infusion system, the induction phase of anesthesia and the maintenance phase of anesthesia.
- Effect of drugs delivery on heart rate. It is assessed by means of the percentage of the anesthesia maintenance duration in which the heart rate (HR) is kept inside the range from 50 to 100 beats per minute. The percentage of the anesthesia maintenance duration in which the HR is kept below 50 is also specified.
- Effect of drugs delivery on mean blood pressure. It is assessed by means of the percentage of the anesthesia maintenance duration in which the non-invasively measured mean blood pressure (MBP) is kept inside the range from 65 to 110 mmHg. The percentage of the anesthesia maintenance duration in which the MBP is kept below 65 is also specified.
- Postoperative heart rate stability. It is assessed by measuring the HR in bpm.
- Postoperative Mean Blood Pressure Stability. It is assessed by non-invasive measuring of the mean blood pressure in mmHg.

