## Subject Enrollment Count

All subjects enrolled in the clinical investigation (including patients withdrawn from the study before its initiation who have provided informed consent and patients lost to follow-up) must be counted and documented. If a subject withdraws from the study, the reasons should be documented and recorded. These patients will not be included in the sample size calculation for the study or in the primary or secondary objectives.

Patients who are withdrawn from the study before the initiation of the ACTIVA software due to device safety, reliability, or feasibility issues are considered enrolled in the study and will be followed throughout the study's duration.

Patients who discontinue the study during the operation of the ACTIVA software are considered fully enrolled, and all available data will be analyzed.

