### Selection bias at the time of analysis.

The clinical trial requires that closed-loop anesthesia be practiced from the initiation of the ACTIVA software until the end of the surgical procedure. However, it may happen that:

- The primary experimenter decides to interrupt the software; in this case, it must be recorded in the report file.
- The software or its components (monitors, infusion pumps) may cease to function correctly; in this case, the system is halted and switches to manual mode or requires the experimenter's intervention. The experimenter must record the event in the report file. If the above occurs, it is the responsibility of the experimenter to assess the possibility of including in the data analysis what has been collected up to the moment of system interruption.

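### If followed, the Protocol's rule on incomplete patients removes session-ending software failures from the dysfunction outcome; two other Protocol rules conflict with it, and the SAP does not choose between them

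*Protocol*

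**What the plan says.** **The exclusion.** Protocol, Deviations from the clinical evaluation plan: cases in which an enrolled patient "does not complete the study due to ACTIVA software issues or at the investigator's discretion are not considered deviations", and for such cases "the patient will not be considered for secondary outcome measures but will be evaluated for the primary outcome measure".

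**The outcome and its objective.** Protocol, Clinical study description, and SAP, Outcomes, both list first among the secondary outcomes: "Number and types of dysfunctions of the ACTIVA automatic infusion system". Neither makes an exception for interrupted sessions. Protocol, Clinical study objectives: "The secondary objective is to evaluate the reliability, safety and applicability of the control system under study".

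**Two other rules for interrupted sessions.** Protocol, Subject Enrollment Count: "Patients who discontinue the study during the operation of the ACTIVA software are considered fully enrolled, and all available data will be analyzed". Protocol, Selection bias at the time of analysis, on sessions stopped by the experimenter or by a malfunction: "it is the responsibility of the experimenter to assess the possibility of including in the data analysis what has been collected" up to the interruption.

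**Recording.** Protocol, Predicted clinical risks: "The ACTIVA software always generates a report file, even in the case of malfunctions". On monitor and pump faults, the section on factors that may compromise the results says: "These malfunctions are not attributed to the ACTIVA software but will be recorded in the report file and evaluated during the results analysis".

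**The SAP.** Its section on the population to be analysed repeats the recruitment and conduct text. Its Analyses section promises descriptive statistics for every study variable. Neither defines an analysis set or a rule for interrupted sessions.

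**The concern.** A software problem that stops a patient from completing is both a trigger for exclusion and an event that the dysfunction outcome is meant to count. A summary built on this rule is a completers-only summary, selected on the outcome itself. It would look clean for session-ending software failures however often they occurred.

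The second trigger, the investigator's discretion, widens the effect. The Protocol allows the experimenter to switch to manual control when BIS cannot be held in range, and also when nothing has malfunctioned. Those patients would leave every secondary outcome too: satisfaction, heart rate, blood pressure, sedation, nausea and vomiting, and pain.

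The Protocol calls this the first clinical investigation of the system, and the SAP's introduction says the purpose is to demonstrate that the system is reliable, safe and applicable. Session-ending failures bear directly on that claim. With three rules in the Protocol and none in the SAP, the analysis set could also be chosen after the results are known.

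**Working it through.** **1. The denominator.** The plan's 139 patients serve only as the denominator here. With n = z²p(1−p)/h², z = 1.96 and p = 0.90, a half-width h = 0.05 gives 138.3, rounded up to 139; h = 0.10 gives 34.6, rounded up to 35. So 139 is reproduced if the stated 10% is read as the full width of the interval. That wording is a separate matter and does not affect this point.

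**2. The three rules side by side, for a patient whose session is ended by a software crash.**

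| Protocol section | Primary outcome | Secondary outcomes |
|---|---|---|
| Deviations | included | excluded |
| Subject Enrollment Count | all available data | all available data |
| Selection bias at the time of analysis | experimenter decides | experimenter decides |

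The rules cannot all be followed.

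**3. Session-ending software failures under the Deviations rule.** Let N = 139 and let k patients have a session ended by a software issue. Counted over everyone, the rate is k/N. Under the rule these k patients leave both numerator and denominator, so the reported figure is 0/(N−k) for every k. The documents give no value for k, so a range is assumed. Intervals are two-sided exact (Clopper-Pearson) 95%; with zero events the upper limit is 1 − 0.025^(1/(N−k)).

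| Assumed rate | All patients, k/139 (95% CI) | Under the rule | Upper 95% limit |
|---|---|---|---|
| 1% | 1/139 = 0.7% (0.0 to 3.9%) | 0/138 | 2.6% |
| 2% | 3/139 = 2.2% (0.4 to 6.2%) | 0/136 | 2.7% |
| 5% | 7/139 = 5.0% (2.0 to 10.1%) | 0/132 | 2.8% |
| 10% | 14/139 = 10.1% (5.6 to 16.3%) | 0/125 | 2.9% |
| 20% | 28/139 = 20.1% (13.8 to 27.8%) | 0/111 | 3.3% |

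At 5% and above, the reported interval excludes the assumed rate. At 1% and 2% it does not, although the count is still wrong.

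**4. All dysfunctions together.** Suppose 7 sessions end through a software issue and 7 other patients have a dysfunction that is resolved. Over all patients the rate is 14/139 = 10.1%; under the rule it is 7/132 = 5.3%. With 10 and 10, it is 20/139 = 14.4% against 10/129 = 7.8%.

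**5. Satisfaction.** Suppose 10 failed sessions score 3 and the other 129 score 8. The mean over all patients is (129×8 + 10×3)/139 = 1062/139 = 7.6; under the rule it is 8.0. The scores are assumed. The direction depends only on failed sessions scoring lower on average, which is likely but not given.

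**6. Other secondary outcomes.** No direction can be derived. Discretionary stops may occur without a malfunction, and after a switch the postoperative findings partly reflect manual control.

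**The case against.** **The exclusion is not the settled rule.** Subject Enrollment Count requires all available data to be analysed. The later-dated SAP (17/06/2020, against a protocol version of 07/03/2019) promises summaries of all variables, lists dysfunctions and satisfaction among the data collected, and states no exclusion. This stands: the documents contradict themselves, and the bias follows only if the Deviations rule is applied. But the SAP's general sentence names no analysis set and does not overrule the specific clause.

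**Completing the study could mean reaching the 24-hour visit.** The Protocol ends participation there, so a patient switched to manual control who attends that visit might be outside the clause. The wording is ambiguous, but this reading does not rescue it. The clause names software issues as a cause of non-completion and keeps the patient for a primary outcome measured during maintenance, so it must reach sessions that started and were cut short.

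**The failures do not vanish.** A reader might infer that session-ending failures go unrecorded. The documents do not support that. The report file is always produced, interruptions must be noted, safety notes are reviewed monthly, serious adverse events are reported separately, and reliability problems can suspend or end the study. None of these is the secondary-outcome summary, though.

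**Not every session-ending failure is covered.** The outcome concerns the whole infusion system, whereas the clause names software. Monitor and pump faults are expressly not attributed to the software, so they leave the count only if handled as a discretionary stop. This stands, and the zero count above applies to software failures only.

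**The outcomes are secondary and descriptive, and the primary outcome keeps these patients.** True, but reliability and safety are judged on these descriptive figures.

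**Conclusion.** The point holds conditionally. If the Deviations rule is followed, dysfunctions that end a session through a software issue drop out of the dysfunction summary and the reported rate is biased downward. The size depends on a failure rate that the documents do not give: an assumed 7/139 (5.0%) would appear as 0/132 with an upper 95% limit of 2.8%. Satisfaction is likely biased upward.

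It is tempting to conclude that all the secondary results would favour the device. The documents do not support this for heart rate, blood pressure or the postoperative outcomes, where the direction is uncertain. Nor do they show that the plan has settled on exclusion, since two other incompatible rules stand beside it. The three sections must be reconciled, and the SAP must state the result.

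This rests on reading non-completion to include sessions cut short during surgery, and on the assumed counts for the size.

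**What to change.** - **Protocol, Deviations:** delete the exclusion from secondary outcomes.
- **Protocol, Selection bias at the time of analysis:** replace the experimenter's discretion with the rule in Subject Enrollment Count. Deleting the Deviations clause alone would leave this conflict in place.
- **SAP, dysfunctions and satisfaction:** state that both are summarised over every patient in whom ACTIVA was started, whether or not the session was completed. Report session-ending dysfunctions and discretionary stops on separate lines, by reason.
- **SAP, heart rate and blood pressure:** summarise up to the moment automatic control is turned off, for whatever reason. The present definition of maintenance ends when control is turned off at the conclusion of surgery, which leaves the denominator undefined for an interrupted session.
- **SAP, postoperative outcomes:** show them for all patients, and separately for interrupted sessions, because these partly reflect manual control.

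The cost is a few sentences in each document and slightly more analysis work. No new data should be needed for the intraoperative summaries, because the report file is generated even when the system malfunctions. The dysfunction and satisfaction figures may look less favourable. The change concerns analysis only and does not affect how patients are managed.

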## Number of patients enrolled

The sample size was determined based on the primary outcome measure concerning the depth of hypnosis adequacy provided by the ACTIVA control software. Specifically, it was calculated with the aim to assess the proportion of patients for whom the percentage of the anesthesia maintenance duration in which the BIS is kept inside the recommended range from 40 to 60 is greater than 43%. This latter value is the average percentage that was observed in a previous data acquisition campaign concerning manually controlled TIVA, which was performed in the same clinical setting considered for the present clinical trial (Study acronym: ACTIVA 1, Id code: NP-1843).

The proportion was estimated to be 90% of patients with a 95% confidence interval and a margin of error of 10%. The resulting sample size is 139 patients. This number of enrolled subjects also ensures that the ACTIVA control software is adequately tested for safety, reliability, feasibility, and applicability. Secondary outcome measures were not considered in the sample size calculation.

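### A session in which automatic control ends before induction is complete has no defined primary value, and the plan's three rules on interrupted sessions conflict

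*Protocol*

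**What the plan says.** The Protocol, under Deviations from the clinical evaluation plan, states: "Cases where a regularly enrolled patient does not complete the study due to ACTIVA software issues or at the investigator's discretion are not considered deviations". For such a patient it adds that "the patient will not be considered for secondary outcome measures but will be evaluated for the primary outcome measure".

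The primary outcome (Protocol, Clinical study description; repeated in SAP, Outcomes) is the share of maintenance time with BIS from 40 to 60. Maintenance runs "from the end of anesthesia induction to the point at which the automatic control is turned off at the conclusion of surgery", and induction ends at "the time instant when the BIS drops below 40 for the first time and remains there for the subsequent 30 seconds". The secondary outcomes in the same section include "Number and types of dysfunctions of the ACTIVA automatic infusion system" and the experimenter's satisfaction with the induction phase.

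Automatic control is running before that window opens: "The clinical trial requires that closed-loop anesthesia be practiced from the initiation of the ACTIVA software until the end of the surgical procedure".

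Two other Protocol sections also cover interrupted sessions. Subject Enrollment Count treats patients who stop while the software is running as fully enrolled and has all their available data analysed. Selection bias at the time of analysis leaves it to the experimenter whether data collected before an interruption enter the analysis.

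The sample size (Protocol, Number of patients enrolled; SAP, Sample size calculation) was set to "assess the proportion of patients for whom the percentage of the anesthesia maintenance duration in which the BIS is kept inside the recommended range" exceeds 43%. The SAP's Population to be analyzed section restates eligibility and procedure, and its Analyses section is descriptive. Neither mentions interrupted sessions.

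**The concern.** The Deviations rule sends a non-completing patient to the one outcome that may not exist for that patient, and takes the patient out of the outcomes where the stop would be seen. A controller abandoned during induction matters here: the SAP's Introduction gives the ability to induce anesthesia as part of the purpose, and the secondary objective covers induction.

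Such stops are foreseeable. The Protocol allows a switch to manual control after a software or pump fault, after a BIS signal problem lasting more than 30 seconds, when BIS cannot be held in range, or at the experimenter's discretion at any time. None of these is confined to maintenance. Some will occur because control was poor, so leaving them out is unlikely to be neutral. At stake is whether the reported results describe all sessions in which the system was started, or only those that got past induction.

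**Working it through.** **1. What each rule does with a session stopped during induction**

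| Protocol section | Primary outcome | Secondary outcomes |
|---|---|---|
| Deviations from the clinical evaluation plan | Evaluated, but no maintenance time exists | Removed, including dysfunctions |
| Subject Enrollment Count | All available data, but no maintenance time exists | Kept |
| Selection bias at the time of analysis | Experimenter decides; no maintenance time exists | Experimenter decides |

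No row gives the primary percentage a value, because its denominator is zero in all three. The secondary column differs from row to row, and the SAP does not say which row applies.

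**2. The plan's own sample size**

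Inputs (Protocol, Number of patients enrolled): expected proportion p = 0.90, 95% confidence, margin 10%, n = 139. The formula is n = 1.96² × p(1 − p) / d².

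- d = 0.05 (the 10% taken as the full width of the interval): n = 138.29, rounded up to 139. This reproduces the plan.
- d = 0.10 (plus or minus 10 points): n = 34.57, rounded up to 35. This does not.

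The half-width with 139 patients at 90% is therefore 1.96 × √(0.90 × 0.10 / 139) = 4.99, or about 5.0 points.

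**3. Effect on the proportion above 43%**

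Let k of 139 started sessions end before the end of induction, and let 90% of the other 139 − k exceed 43%.

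- Stops omitted: the estimate is 90%.
- Stops counted as not exceeding 43%: 0.90 × (139 − k) / 139.
- Difference: 0.90 × k / 139.

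The documents give no value for k, so the range is assumed.

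| k | Share of 139 | Omitted | Counted | Shift (points) |
|---|---|---|---|---|
| 2 | 1.4% | 90.0% | 88.7% | 1.3 |
| 5 | 3.6% | 90.0% | 86.8% | 3.2 |
| 8 | 5.8% | 90.0% | 84.8% | 5.2 |
| 10 | 7.2% | 90.0% | 83.5% | 6.5 |

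The shift equals a 5.0-point half-width at a stop rate of 5.0 / 0.9 = 5.6%. Whole-patient counts agree: with 7 stops, 119/132 = 90.2% against 119/139 = 85.6%.

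**The case against.** A reader might infer that the plan drops these sessions from every result and so biases the headline result upward. The documents do not support that as a settled fact, for four reasons.

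- The Deviations rule keeps the patient in the primary evaluation. What is missing is the score. Omission, and with it the upward shift, would be the analyst's choice.
- Under Subject Enrollment Count the stop would stay in the dysfunction count, and it is recorded in the report file in any case.
- The Deviations rule concerns a patient who does not complete the study. Participation runs to the 24-hour visit, so a patient switched to manual control may still complete it and fall outside that rule. Monitor and pump faults are not attributed to the software.
- The proportion above 43% appears only in the sample-size text. The analysis sections provide a mean or median of the percentage.

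It can also be said that the primary outcome is about maintenance, that some stops reflect sensor adhesion or preference, and that scoring them as failures is one convention among several. Start-up checks and tolerance of short BIS loss may keep such stops rare.

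All of this limits the claim. It does not supply a primary value for the session or reconcile the three rules. If only the continuous percentage is reported, these patients are still absent from it.

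**Conclusion.** The point holds in a limited form. A session in which automatic control was started and ended before the end of induction has no primary percentage under any of the three rules, and neither document says how to score it. Applying the Deviations rule and omitting undefined values would leave the session out of every outcome result, though not out of the study record. The other two sections point elsewhere, and the SAP leaves the conflict open.

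The size is conditional. It assumes that 90% of the remaining patients exceed 43%, that undefined values are omitted, and that the proportion above 43% is reported. The shift is then about 0.9 times the induction-stop rate, and it passes the 5.0-point half-width at 8 of 139 sessions. With no stop rate in the documents, the actual shift is unknown and could be negligible.

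**What to change.** Reconcile the three Protocol sections in the SAP's Population to be analyzed with one rule that leaves nothing to the experimenter's discretion at analysis:

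- Keep every patient in whom automatic control was started in the denominator of the proportion above 43%. Count control that ended before the end of induction as not exceeding 43%.
- Add a sensitivity analysis excluding these patients.
- Report their number and the reasons beside the primary result.
- Summarise the continuous percentage only for patients with a maintenance window, and show that n.
- Keep dysfunctions and early stops in the secondary results for all started sessions.

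The cost is SAP wording, matching edits to the Protocol, and an extra row or two in the primary table. The proportion may come out slightly less favourable, and some counted stops (sensor, pump or monitor faults) will not be attributable to the software. The listed reasons and the sensitivity analysis let the reader judge that. No change to clinical conduct is involved.
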